8.4.3 Visit 2: Day 1 – Confirmation and Baseline

- Placebo Collection: All used/unused placebo ampoules dispensed for Days –14 to 1 should be collected and reviewed by a trained study technician.
- Site staff must confirm subjects have NOT administered their morning placebo dose at home. If subject dosed prior to the visit, study visit procedures should begin 4 hours after time of dosing.
- Monitoring and Query of AEs: Report any AEs that occur after signing the ICF.
- Record all Changes in Concomitant Medications
- Ora Calibra® Ocular Discomfort Scale
- Ora Calibra® Ocular Discomfort & 4-Symptom Questionnaire
- VAS
- OSDI®
- BCVA Utilizing an ETDRS Chart
- Slit-Lamp Biomicroscopy
- Conjunctival Redness
- TFBUT
- Corneal and Conjunctival Staining (fluorescein)
- Corneal and Conjunctival Staining (lissamine green)
- Schirmer's Test

- Review of Inclusion and Exclusion Criteria

- Report a score of █ according to the Ora Calibra® Ocular Discomfort & 4-Symptom Questionnaire in at least one of the dry eye symptoms at Visits 1 and 2
- *Eligible subjects must have a positive response in at least one eye. A positive response is defined as meeting ALL of the following criteria in the same eye:*
 - Report a score of █ according to the Ora Calibra® Ocular Discomfort & 4-Symptom Questionnaire in at least one of the dry eye symptoms at Visit 1 and 2
 - Have a Schirmer's Test score of ≤ 10 mm and ≥ 1 mm in at least one eye at Visits 1 and 2
 - Have a corneal fluorescein staining score █ according to the Ora Calibra® Corneal and Conjunctival Staining Scale for Grading of Fluorescein Staining in at least one of the corneal regions █ in at least one eye at Visits 1 and 2
 - Have a CCSS of █ according to the Ora Calibra® Corneal and Conjunctival Staining Scale for Grading of Fluorescein Staining in at least one eye at Visit 2
 - Have a CCSS at Visit █ to CCSS at Visit 1
 - Have a conjunctival redness score █ according to the Ora Calibra® Conjunctival Redness for Dry Eye Scale in at least one eye at Visits 1 and 2
 - Have at least one eye, the same eye, satisfy all inclusion criteria for 8, 9, 10, 11, 12 and 13
- Note: If only one eye qualifies then the single qualifying eye will be the study eye. In the case that both eyes are eligible for analysis, the study eye will be the eye with worse (higher) central corneal fluorescein staining at Visit 2. If the central corneal fluorescein staining is the equivalent in both eyes, then the right eye will be selected as the study eye.
- **Randomization** – subjects will be randomized according to the following two strata:
 1. Visit 2 study eye CCSS █ and
 2. Visit 1 CCSS minus Visit 2 CCSS (V1 CCSS - V2 CCSS); difference in study eye CCSS █
- **Blood Sampling** Blood samples will be collected from all subjects for immunogenicity testing █

- Study Drug Instillation at the Study Site All subjects meeting all other screening eligibility criteria after Visit 2 will be randomized to one of two treatment arms. Randomized subjects will self-administer their initial study drug dose bilaterally at the study site.
- Ora Calibra® Drop Comfort Assessments The Ora Calibra® Drop Comfort Scale will be performed immediately after instillation and then at 1, 2, and 3 minutes following instillation.
- Monitoring and Query of AEs
- Study Drug Dispensation Prior to discharge from the study site on Visit 2 (Day 1), randomized subjects will be educated in the self-administration of study drug. The initial, self-administered dose taken in-office at Visit 2 will be counted as a morning dose regardless of visit time, and subjects will be instructed to administer an evening dose that night. Subjects will receive their assigned study drug kit with sufficient supply to last until Visit 3 and will be instructed NOT to self-administer study drug on the morning of their next scheduled study visit (Visit 3, Day 8).
- Schedule Next Visit Subjects will be scheduled for Visit 3.

8.4.4 Visit 3: Day 8 ± 1 –Week 1

- Study Drug Collection All used/unused study drug vials dispensed for Days 1 to 8 should be collected and reviewed by a trained study technician.
- Site staff must confirm that subjects have NOT administered their morning study drug dose at home. If subject dosed prior to the visit, study visit procedures should begin 4 hours after time of dosing.
- Monitoring and Query AEs
- Recording of all Changes in Concomitant Medications
- Ora Calibra® Ocular Discomfort Scale
- Ora Calibra® Ocular Discomfort & 4-Symptom Questionnaire
- VAS
- OSDI[©]
- BCVA Utilizing an ETDRS Chart
- Slit-Lamp Biomicroscopy
- Conjunctival Redness
- TFBUT
- Corneal Staining and Conjunctival (fluorescein)
- Corneal and Conjunctival Staining (lissamine green)

- [REDACTED]
- Study Drug Instillation at the Study Site Subjects will self-administer their first study drug dose bilaterally for Day 8 at the study site following the last study assessment. The evening dose will be administered at home, by the subject.
- Ora Calibra® Drop Comfort Assessment The Ora Calibra® Drop Comfort Scale will be performed immediately and then at 1, and 2 minutes following initial dosing. At 3 minutes following the initial drop, the Ora Calibra® Drop Comfort Questionnaire will be performed.
- Study Drug Re-Dispensation Prior to discharge from the study site on Visit 3 (Day 8), study drug kits from Visit 2 (Day 1) will be re-dispensed to subjects with the remaining study drug to complete up to Visit 4 (Day 15). Subjects will again be educated on self-administration of study drug. Subjects will be instructed to NOT self-administer study drug on the morning of their next scheduled study visit (Visit 4, Day 15).
- Schedule Next Visit Subjects will be scheduled for Visit 4.

8.4.5 Visit 4: Day 15 ± 2 –Week 2

- Study Drug Collection All used/unused study drug vials dispensed for Days 8 to 15 should be collected and reviewed by a trained study technician.
- Site staff must confirm subjects have NOT administered their morning study drug dose at home. If subject dosed prior to the visit, study visit procedures should begin 4 hours after time of dosing.
- Monitor and Query AEs
- Record all Changes in Concomitant Medications
- Ora Calibra® Ocular Discomfort Scale
- Ora Calibra® Ocular Discomfort & 4-Symptom Questionnaire
- VAS
- OSDI[©]
- BCVA Utilizing an ETDRS Chart
- Slit-Lamp Biomicroscopy
- Conjunctival Redness
- TFBUT
- Corneal and Conjunctival Staining (fluorescein)
- Corneal and Conjunctival Staining (lissamine green)
- Schirmer's Test

- [REDACTED]
- Study Drug Dispensation Prior to discharge from the study site on Visit 4 (Day 15), subjects will be educated on self-administration of study drug. Subjects will receive their new assigned study drug kit with sufficient supply to last until Visit 5 and will be instructed to NOT self-administer study drug on the morning of their next scheduled study visit (Visit 5, Day 29). Subjects will self-administer morning dose after visit is complete, regardless of the time, and instructed to administer an evening dose that night.
- Schedule Next Visit Subjects will be scheduled for Visit 5.

8.4.6 Visit 5: Day 29 ± 2 –Week 4

- Study Drug Collection All used/unused study drug vials dispensed for Days 15 to 29 should be collected and reviewed by a trained study technician.
- Site staff must confirm subjects have NOT administered their morning study drug dose at home. If subject dosed prior to the visit, study visit procedures should begin 4 hours after time of dosing.
- Monitoring and Query of AEs
- Record all Changes in Concomitant Medications
- Ora Calibra® Ocular Discomfort Scale
- Ora Calibra® Ocular Discomfort & 4-Symptom Questionnaire
- VAS
- OSDI[®]
- BCVA Utilizing an ETDRS Chart
- Slit-Lamp Biomicroscopy
- Conjunctival Redness
- TFBUT
- Corneal and Conjunctival Staining (fluorescein)
- Corneal and Conjunctival Staining (lissamine green)
- Schirmer's Test
- [REDACTED]
- Monitoring and Query of AEs

- Study Drug Dispensation Prior to discharge from the study site on Visit 5 (Day 29), subjects will be educated in on self-administration of study drug. Subjects will receive two new assigned study drug kits with sufficient supply to last until Visit 6 and will be instructed to NOT self-administer study drug on the morning of their next scheduled study visit (Visit 6, Day 57 ± 3). Subjects will self-administer morning dose after visit is complete, regardless of the time, and instructed to administer an evening dose that night.

- Schedule Next Visit Subjects will be scheduled for Visit 6.

8.4.7 **Visit 6: Day 57 ± 3 –Week 8 and Study Exit**

- Study Drug Collection All used/unused study drug vials dispensed for Days 29 to 57 should be collected and reviewed by a trained study technician.
- Site staff must confirm subjects have NOT administered their morning study drug dose at home. If subject dosed prior to the visit, study visit procedures should begin 4 hours after the time of dosing.
- Monitoring and Query of AEs
- Record all Changes in Concomitant Medications
- Urine Pregnancy Test (for females of childbearing potential)
- Ora Calibra® Ocular Discomfort Scale
- Ora Calibra® Ocular Discomfort & 4-Symptom Questionnaire
- VAS
- OSDI[©]
- BCVA Utilizing an ETDRS Chart
- Slit-Lamp Biomicroscopy
- Conjunctival Redness
- TFBUT
- Corneal and Conjunctival Staining (fluorescein)
- Corneal and Conjunctival Staining (lissamine green)
- Schirmer's Test
- Intraocular Pressure
- Dilated Fundoscopy
- Blood Sampling for Immunogenicity Testing [REDACTED]
- Study Exit

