
The primary analysis of the primary endpoints will use the ITT population with multiple imputation methodology as specified in Estimand 1 using Mixed Model for Repeated Measures (MMRM) if the rate of missing data for an endpoint is balanced between the two treatment groups or the rate of missing data for an endpoint is less than 10% in all subjects. If the rate of missing data for an endpoint is imbalanced between treatment groups and the rate of missing data for an endpoint is $\geq 10\%$ in all subjects, then the primary analyses will utilize the ITT population with single imputation methodology specified in Estimand 2 using the permutation test with trimmed means methodology (Permutt et al., 2017).
 
The MMRM will be used to compare the change from baseline (V2) to Day 57 ± 3 (V6, Week 8) for CCSS between tanfanercept ophthalmic solution 0.25% and placebo. The initial model will include terms for baseline CCSS, site, visit (as categorical term), treatment group, and the interaction of treatment group and visit as fixed effects with correlated errors. An unstructured covariance matrix will be initially fit with the model. Should an unstructured covariance matrix fail to achieve convergence then alternate covariance structures will be attempted to be detailed in the Statistical Analysis Plan (SAP). The inclusion of site in the final model will be evaluated at an alpha level of 0.1. All post-baseline visits will be used in the model. In addition, the site by treatment interaction will be explored in a separate model to evaluate how the treatment effect may differ across sites.
 
Change from baseline of EDS from VAS at Day 57 ± 3 (V6, Week 8) between tanfanercept ophthalmic solution 0.25% and placebo will be analyzed as described for CFB of CCSS with adjustment for baseline EDS instead of baseline CCSS.
 
An alternate MMRM will be executed as supportive analysis for both primary endpoints. These additional models will include all terms in the final models of the primary analyses with [REDACTED]
 
[REDACTED]
 
Sensitivity analyses will include imputation by Last Observation Carried Forward (LOCF), multiple imputation by placebo group-based pattern mixture models (PMM), and analyses of observed data only using the ITT and PP populations will also be conducted.
 
Two-sample t-tests will also be conducted as supportive analyses of the mean change from baseline at Day 57 ± 3 (V6, Week 8).
 
Additional exploratory comparisons of the mean absolute scores of the primary endpoints at both Day 57 ± 3 (V6, Week 8) and baseline (V2) between the treatment groups will be conducted using two-sample t-tests and MMRM.
	

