If the rate of missing data for an endpoint is imbalanced between treatment groups (demonstrated by Fisher's exact test with a p-value of <0.05) and the rate of missing data for an endpoint is $\geq 10\%$ in all subjects, then the primary analyses will utilize the ITT population with single imputation methodology specified in Estimand 2 using the permutation test with trimmed means methodology.

Estimand 2:

- Population:
 - ITT population

- Endpoint:
 - CFB in CCSS in the study eye at Day 57 ± 3 in the ITT population
 - CFB in EDS from VAS at Day 57 ± 3 in the ITT population
- Intercurrent event:
 - Discontinuation of study medications is ignored. Measures obtained after discontinuation of study medication will be analyzed [treatment policy strategy]
 - Non-optimal compliance is ignored. Measures will be analyzed regardless of treatment compliance [treatment policy strategy]
 - Use of prohibited concomitant medications is ignored. Measures obtained after use of prohibited concomitant medications will be analyzed [treatment policy strategy]
 - Withdrawal or missed assessments for any reason. Missing values will be singly imputed using randomized treatment group-based worst observed value imputation [hypothetical strategy]. Note: imputed values will ultimately be trimmed from analyses per trimmed means methodology.
- Population-level summary:
 - Difference in the mean CFB in CCSS in the study eye at Day 57 ± 3 between tanfanercept and placebo in the ITT population

The proportion of data trimmed in the permutation test with trimmed means analysis will be dependent on the maximum rate of missing data in any treatment group using the following:

Maximum Rate of Missing Data (%)	Data Trimmed (%)
10% to <20%	20%
20% to <30%	30%

MMRM will be used to compare the change from baseline in CCSS at Day 57 ± 3 (V6, Week 8), as measured on the Ora Calibra® scale, between Tanfanercept Ophthalmic Solution 0.25% and Placebo. The MMRM will include terms for baseline in CCSS, site, visit, treatment group, and the interaction of visit and treatment group as fixed effects with correlated errors. An unstructured covariance matrix will be initially fit with the model. Should an unstructured covariance matrix fail to achieve convergence then alternate covariance structures will be attempted to be detailed in the Statistical Analysis Plan (SAP). The inclusion of site in the final model will be evaluated at an alpha level of 0.1.

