If site is retained in the final primary analyses, the site by treatment interaction will be explored in a separate analysis to evaluate how the treatment effect may differ across sites. All post-baseline visits will be used in the model. Two-sample t-tests will also be conducted as supportive analyses.

Change from baseline of EDS from VAS at Day 57 ± 3 (V6, Week 8) between tanfanercept ophthalmic solution 0.25% and placebo will be analyzed as described for CFB of CCSS with adjustment for baseline EDS instead of baseline CCSS.

Example SAS code for the MMRM of the primary analyses is as follows:

```
PROC MIXED DATA = INDATA METHOD = REML;  
  CLASS SUBJID TREATMENT VISIT SITE;  
  MODEL CHG = BASELINE SITE VISIT|TREATMENT / DDFM = KR SOLUTION COVB;  
  REPEATED VISIT/SUBJECT = SUBJID TYPE = UN R RCORR;  
  LSMEANS TREATMENT TREATMENT*VISIT / CL PDIFF;  
RUN;
```

where

- *SUBJID* is the subject ID
- *TREATMENT* is the name of the treatment group variable
- *VISIT* is the visit
- *SITE* is the site id
- *CHG* is the change from baseline
- *BASELINE* is the baseline value

An alternate MMRM will be executed as a sensitivity analyses for both primary endpoints. These additional models will include all terms in the final models of the primary analyses.

Additional exploratory comparisons of the mean absolute scores of the primary endpoints at both Day 57 ± 3 (V6, Week 8) and baseline (V2) between the treatment groups will be conducted using two-sample t-tests and MMRM.

Least squares means and standard errors for each treatment group and for the difference between treatment groups will be presented from the MMRM together with two-sided p-values and 95% confidence intervals. Two-sided exact p-values and 95% confidence intervals will be presented from the permutation test with trimmed means.

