13.1.1 CENTRAL CORNEAL STAINING SCORE (CCSS)

CCSS CFB to Day 57 will be analyzed using the ITT population with multiple imputation methodology specified in Estimand 1 ([Section 2.6](#)). The initial MMRM model will include terms for baseline CCSS, site, visit (as categorical term), treatment group and the interaction of treatment group and visit as fixed effects with correlated errors. The inclusion of site in the final model will be evaluated at an alpha level of 0.1. All post-baseline visits will be used in the model.

If site is retained in the final primary analyses, the site by treatment interaction will be explored in a separate analysis to evaluate how the treatment effect may differ across sites. All post-baseline visits will be used in the model.

An alternate MMRM will be executed as supportive analysis. This additional model will include all terms in the final model of the primary analyses with, [REDACTED]

Sensitivity analyses to compare CCSS CFB between treatment groups using imputation by Last Observation Carried Forward (LOCF), multiple imputation by placebo group-based pattern mixture models (PMM), and analyses of observed data only using the ITT and PP populations will be conducted.

The Least Square (LS) means, LS mean difference, Standard Errors (SEs), two-sided 95% CIs, and p-values of the LS mean difference will be reported from the MMRM model. Two-sample t-tests will also be conducted as supportive analyses of the mean CFB to Day 57. The sample means, sample mean difference, SEs, two-sided 95% CIs, and two-sided p-values will be reported from the two-sample t-test.

The MMRM LS means of the CCSS CFB in the study eye at Day 57 and CCSS CFB at each visit will be displayed graphically in a bar chart with SE bars by treatment group.

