13.1.2 EYE DRYNESS SCORE ON VISUAL ANALOG SCALE (EDS-VAS)

EDS-VAS CFB to Day 57 will be analyzed as described above for the analysis of CCSS with adjustment for baseline EDS-VAS instead of CCSS. Estimand 2 will be used for the analysis of EDS-VAS in the presence of an imbalance of missing data between the two treatment groups ([Section 2.6](#)).

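### The listed primary models leave out stratification factors (V1-V2 CCSS change for CCSS, both factors for EDS), which at most makes the tests slightly conservative

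*Protocol*

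**What the plan says.** **Allocation.** Under the Visit 2 procedures, Protocol 8.4.3 states that "subjects will be randomized according to the following two strata". The factors are Visit 2 study-eye CCSS and the study-eye difference V1 CCSS minus V2 CCSS. The cut-points are redacted. No block structure is described, and SAP 4.1, on assignment to treatment, does not mention stratification.

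**Primary CCSS model.** Three texts and one code block list the same terms:
- Protocol synopsis: "The initial model will include terms for baseline CCSS, site, visit (as categorical term), treatment group, and the interaction of treatment group and visit".
- Protocol 10.4.5: "The MMRM will include terms for baseline in CCSS, site, visit, treatment group, and the interaction of visit and treatment group".
- Protocol 10.4.5, example code: "MODEL CHG = BASELINE SITE VISIT|TREATMENT / DDFM = KR SOLUTION COVB".
- SAP 13.1.1: "The initial MMRM model will include terms for baseline CCSS, site, visit (as categorical term), treatment group and the interaction" (of treatment group and visit).

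Site stays in the final model only if it passes a test at 0.1.

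**Primary EDS model.** It follows the CCSS model "with adjustment for baseline EDS instead of baseline CCSS" (Protocol 10.4.5), or "with adjustment for baseline EDS-VAS instead of CCSS" (SAP 13.1.2).

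**Alternate model.** SAP 13.1.1 adds: "An alternate MMRM will be executed as supportive analysis". Its extra terms are redacted. The protocol synopsis also calls it supportive, and Protocol 10.4.5 calls it a sensitivity analysis.

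**Imputation.** The visible CCSS code in SAP Appendix 1 imputes from baseline and Visits 3 to 6, by treatment or from placebo. It has no stratum term.

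**The concern.** Stratified allocation removes chance imbalance between the arms on the strata. To the extent that the strata predict outcome, this reduces the true variability of the treatment difference. A model without the strata leaves their contribution in the residual variance, so its standard error overstates that variability.

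The V1-V2 factor could well predict CCSS. Once Visit 2 CCSS is known, knowing V1-V2 is the same as knowing Visit 1 CCSS, a second pre-treatment reading of the same graded score. If the score carries measurement error, that reading adds information about Week 8.

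What is at stake is efficiency. EDS is the endpoint to look at first: its model has neither factor, the study is powered on the sign endpoint only, and no EDS power is stated.

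**Working it through.** **1. The plan's own power figure.** The SD and difference are redacted, so the standardised difference d is solved from 99.4% power at 135 per arm, two-sided 0.05 (SAP 5):

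d = (1.960 + 2.512) / √(135/2) = 0.544 (0.546 with the t distribution).

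At 119 per arm, k = 0.544 × √(119/2) = 4.20, and power = Φ(4.20 − 1.96) = 98.7%. This matches the SAP.

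**2. Which factors are covered.**

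| Factor | CCSS model | EDS model |
|---|---|---|
| Visit 2 CCSS | covered by continuous baseline | absent |
| V1-V2 CCSS | absent | absent |

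**3. Formulas.** Let e be the proportion by which the unadjusted model SE exceeds the adjusted one, and k the true difference divided by the unadjusted SE. With allocation balanced within strata:
- power without strata = Φ((1+e)(k − 1.96))
- power with strata = Φ((1+e)k − 1.96)
- type I error without strata = 2Φ(−1.96(1+e))

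**4. Size of e for CCSS.** The documents give no prognostic strength, so this was simulated with 600,000 subjects per scenario before eligibility. A Week 8 ANCOVA stands in for the MMRM. Assumptions:
- CCSS on 0 to 4 in steps of 0.5 (the bounds and rounding in SAP Appendix 1), SD 0.8, mean 2.0 or 2.5.
- Binary strata: V2 at least 2.5 or 3.0; V1-V2 above −0.5, 0 or 0.5; at least 10% of subjects per level.
- Eligibility: both visits at least 2, plus one of V2 ≥ V1, V2 ≤ V1 or |V1−V2| ≤ 0.5. Inclusion criterion 12 relates CCSS to its Visit 1 value, but its form is redacted.

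| Between-visit correlation | SE excess e |
|---|---|
| 0.4 | about 0.5 to 1.2% |
| 0.5 | about 0.8 to 1.6% |
| 0.6 | about 1.2 to 2.1% |

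The Visit 2 stratum itself adds less than 0.1 percentage point to the CCSS figure.

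**5. Size of e for EDS.** Assumed: baseline to Week 8 EDS correlation 0.5, V1 to V2 CCSS correlation 0.5, and CCSS equally correlated with baseline and Week 8 EDS. At EDS-CCSS correlations of 0.1, 0.2 and 0.3, e is about 0.1%, 0.1 to 0.5% and 0.4 to 1.2%. The 1.2% comes from a scenario with no eligibility rule; with a V1-V2 rule the top is about 1.0%.

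**6. Power and type I error.** CCSS uses k = 4.20. EDS uses k = 1.960 + 0.842 = 2.80, the value for an assumed 80% power.

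| Endpoint, e | Without strata | With strata | Gain (points) | Type I error without strata |
|---|---|---|---|---|
| CCSS, 1% | 98.81% | 98.87% | 0.06 | 4.8% |
| CCSS, 2.1% | 98.89% | 99.00% | 0.11 | 4.5% |
| EDS, 1% | 80.2% | 80.8% | 0.5 | 4.8% |
| EDS, 1.2% | 80.3% | 80.9% | 0.65 | 4.7% |

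**7. Check by simulated trials.** With 238 subjects, four strata and assumed permuted blocks of 4 (20,000 trials), e = 1% gave 79.9% without and 80.5% with strata at 80% nominal power, and 98.6% and 98.7% at 98.7% nominal. These include the degrees of freedom spent.

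**8. Dependence on balance.** A separate simulation with strongly prognostic factors and unblocked simple randomisation gave type I errors of 4.8% (CCSS) and 5.3% (EDS) without the strata, so no systematic conservatism. Under stratified blocks the same settings gave 3.7% and 3.6%.

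**The case against.** **No decision turns on it.** CCSS has about 98.7% power and gains a tenth of a point at most. The EDS gain is about half a point on a power that the documents never state. This stands, and it sets the weight of the point.

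**Larger figures can be produced.** Without any eligibility rule, the CCSS excess reaches 4.2%. For EDS it reaches 4.6% (2.3 power points) if CCSS correlates with Week 8 EDS but not with baseline EDS. Neither is a fair description: criterion 12 links CCSS to its Visit 1 value, and a correlation that appears only after baseline is implausible. Neither figure is relied on.

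**Redaction limits the conclusion.** The SAP supersedes the protocol's methods, and its MODEL line for the imputed data is redacted. The alternate MMRM's redacted terms may be the strata. A reader might infer that the trial ignores its stratification altogether; the documents do not support that. What can be said is that no visible list of primary terms contains V1-V2, and that the legend under the redacted SAP code names only treatment, site, baseline and change from baseline. If the alternate model holds the strata, the question is only which model is primary.

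**Conservatism is conditional.** It requires allocation that balances the arms within strata. The documents describe no blocking, so this is an assumption. This also stands.

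**Conclusion.** The mismatch is real and minor. The listed primary CCSS model omits the V1-V2 stratum, and the listed primary EDS model omits both strata. If the factors are prognostic and allocation balances within strata, standard errors are about 0.5 to 2.1% too large for CCSS and plausibly 0.1 to 1.2% too large for EDS. These ranges rest on assumed correlations, cut-points and eligibility rules, because the actual values are redacted or not given.

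A reader might infer that leaving out stratification factors biases the estimate or invalidates the primary test. It does neither: the estimate is unbiased, and the type I error is at or below 5%. If the factors are not prognostic, nothing is lost. This is a low-cost efficiency gain to consider, not a threat to validity.

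**What to change.** Before unmasking:
- Add the V1-V2 stratum, as randomised, to the primary CCSS MMRM. A Visit 2 stratum term adds almost nothing there.
- Add both strata, as randomised, to the primary EDS MMRM.
- Keep each endpoint's continuous baseline.
- Include the same terms in the matching imputation and sensitivity models, so that imputation and analysis agree.
- If Estimand 2 is triggered, permute treatment within strata.

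If the alternate MMRM already contains the strata, making it the primary model achieves the main part. If the strata are left out on purpose, the SAP should say why.

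Cost: SAP wording, respecified imputation code (the present PROC MI steps use only numeric scores as predictors, with bounds and rounding) and a few degrees of freedom: 2 if both factors are binary, but the number of levels is redacted. No new data are needed.
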